### **9.3.3. Study Discontinuation**

Both RTI International and the Investigator reserve the right to terminate the study at any time. Should this be necessary, both parties will arrange discontinuation procedures and notify the appropriate regulatory authority(ies) and IRBs. In terminating the study, RTI International and the Investigator will assure that adequate consideration is given to the protection of the participants' interests.

## ABBREVIATIONS

AE	Adverse Event
AHRQ	Agency for Healthcare Research and Quality
AUDIT	Alcohol Use Disorders Identification Test
AUDIT-C	Alcohol Use Disorders Identification Test Alcohol Consumption Questions
BHP	behavioral health provider
CAPS	Clinician-Administered PTSD Scale
CAPS-4	Clinician-Administered PTSD Scale for DSM-IV
CAPS-5	Clinician-Administered PTSD Scale for DSM-5
CBC	complete blood count
CITI	Collaborative Institutional Training Initiative
CRF	Case Report Form(s)
CRO	Contract Research Organization
CRPS	complex regional pain syndrome
CS	Clinical Supervisor
DOD	Department of Defense
DRP	Distressed Respondent Protocol
DSM-5	Diagnostic and Statistical Manual of Mental Disorders , Fifth Edition
DSMB	Data and Safety Monitoring Board
DSM-IV	Diagnostic and Statistical Manual of Mental Disorders , Fourth Edition
ECG	electrocardiogram
ED	emergency department
EEG	electroencephalogram
FDA	(U.S.) Food and Drug Administration
GAD-7	Generalized Anxiety Disorder 7-item Scale
GCP	Good Clinical Practice (Guidelines)
HCT	hematocrit
HGB	hemoglobin
HIPAA	Health Insurance Portability and Accountability Act
HPA	Human Protections Administrator
HRB	Survey of Health Related Behaviors among Active Duty Service Members
HRPO	USAMRMC Office of Research Protections Human Research Protections Office
HSRRB	USAMRMC Office of Research Protections Human Subjects Research Review Board
ICD-10	International Statistical Classification of Diseases and Related Health Problems, 10 th edition
ICF	International Classification of Functioning, Disability and Health
ICH	International Conference on Harmonisation
ICH-GCP	International Conference on Harmonisation Good Clinical Practice
ID	identification
IEC	Independent Ethics Committee
IND	investigational new drug
IOM	Institute of Medicine
IRB	Institutional Review Board
ITT	intent-to-treat (population)
IUD	intrauterine device
IV	intravenous

JAMA	Journal of the American Medical Association
K6	Kessler Psychological Distress Scale
LEC	Life Events Checklist
LRMC	Landstuhl Regional Medical Center
mL	milliliter(s)
MP	Military Police
MRI	magnetic resonance imaging
NCS-R	National Comorbidity Survey Replication
NHIS	U.S. National Health Interview Survey
NSDUH	National Survey on Drug Use and Health
ORP	USAMRMC Office of Research Protections
PAPI	paper-and-pencil interviewing
PCL-5	PTSD Checklist for DSM-5
PCL-C	PTSD Checklist - Civilian
PCL-M	PTSD Checklist - Military
PE	physical examination
PHI	protected health information
PHQ	Patient Health Questionnaire
PHQ-9	Patient Health Questionnaire - 9
PTSD	Posttraumatic Stress Disorder
PVN	paraventricular nucleus of the thalamus
RC	Research Coordinator
RCT	randomized, controlled trial
RSD	reflex sympathetic dystrophy
SAE	Serious Adverse Event
SAP	Statistical Analysis Plan
SF-12	Short Form (12) Health Survey
SF-36	Short Form (36) Health Survey
SG	stellate ganglion
SGB	stellate ganglion block
SOP	Standard Operating Procedure
SPN	sympathetic preganglionic neuron
TAMC	Tripler Army Medical Center
TBI	traumatic brain injury
TV	television
UCMJ	Uniform Code of Military Justice
ULN	upper limit of the normal range
USAMRAA	US Army Medical Research Acquisition Activity
USAMRMC	U.S. Army Medical Research and Materiel Command
USASOC	U.S. Army Special Operation Command
VA	Veterans Administration
WAMC	Womack Army Medical Center

## **BACKGROUND**

Posttraumatic stress disorder (PTSD) is a reaction to a traumatic event in which an individual perceives threat of death or significant injury, resulting in acute fear that is experienced over an extended period of time following the event(s). Symptoms are generally categorized in terms of intrusive symptoms, avoidance, negative alterations in cognitions and mood and alterations in arousal and reactivity (American Psychiatric Association, 2013). PTSD will develop in up to a third of individuals who are exposed to a significant stressor (Committee on Treatment of Posttraumatic Stress Disorder, Institute of Medicine, 2008), and approximately 10% to 20% of those diagnosed with PTSD will become chronic (Fletcher, Creamer, & Forbes, 2010). According to the 2000 National Comorbidity Survey Replication (NCS-R), an estimated 6.8% of adults in the United States will experience PTSD during their lifetime (Dohrenwend et al., 2006). Certain subgroups (e.g., military service members) are at an increased risk because of their higher likelihood of trauma exposure (Jonas et al., 2013). PTSD prevalence among active duty service members ranges from approximately 5% to 15% (Tanielian & Jaycox, 2008). Hoge and colleagues (2004) reported an estimated 12.9% of service members returning from combat operations in Iraq fit diagnostic criteria for PTSD.

There is evidence that the prevalence of PTSD is increasing among service members. The 2008 Department of Defense Survey of Health Related Behaviors among Active Duty Service Members (HRB Survey) found that an estimated 11% met screening criteria for further evaluation of PTSD symptoms, up from 7% in 2005 (Bray et al., 2009). PTSD is also associated with certain mental health disorders, work impairment and decreased earnings, divorce, difficulties with child rearing (R. C. Kessler, 2000), depression and substance use disorders (Brady, Killeen, Brewerton, & Lucerini, 2000).

### **A. PTSD Treatment**

Treatments for PTSD include both psychotherapeutic and pharmacologic modalities, with little existing systematic evidence for effectiveness (Institute of Medicine, 2008). Jonas et al. (2013) found similar results regarding the effectiveness of exposure therapy, and characterized a handful of pharmacologic modalities marginally effective when compared to exposure therapy.

Currently available treatments for PTSD have side effects and varying onset of action (the time required after administration for the treatment for the effect to be observed). Pharmacotherapies side effects include, but are not limited to, nausea, weight gain, headache, sexual dysfunction, and agitation. Symptom relief for this medication take between 6 to 8 weeks of regular use (Alexander, 2012), during which time side effects may develop and discontinuation of the medication(s) may occur. Psychotherapeutic modalities tend to take between 6 to 24 months before the patient experiences significant relief (Sharpless & Barber, 2011). Also, some of the most effective therapies involve exposure to traumatic stimuli which, if improperly applied, may risk further deterioration of the patient (Rauch, Eftekhari, & Ruzek, 2012).

Patient adherence to and acceptability of prescribed treatments also impact treatment effectiveness. Health beliefs (Spoont, Sayer, & Nelson, 2005); knowledge of PTSD and its potential therapies (Gray, Elhai, & Frueh, 2004); and comorbid substance abuse, depression, and other conditions (Kronish, Edmondson, Li, & Cohen, 2012) all play a role in adherence to prescribed treatment regimens.

Several studies demonstrated that stigma associated with receiving treatment is a significant concern for study participants ([name] et al., 2011; Tarrier, Liversidge, & Gregg, 2006) and may result in higher likelihood of treatment failure or discontinuation (Fung, Tsang, & Chan, 2010; Kim, Britt, Klocko, Riviere, & Adler, 2011).

## **B. Stellate Ganglion Block**

Sympathetic blockade, and stellate ganglion block (SGB) in particular, are PTSD treatments that are considered safe, effective, fast-acting, with few side effects, and with good patient acceptability and adherence. SGB is a procedure routinely performed since the 1920s to treat common conditions such as complex regional pain syndrome (CRPS), hot flashes, Raynaud's syndrome, hyperhidrosis, and other sympathetically mediated conditions. The stellate ganglion (SG) is a sympathetic ganglion located at the base of the cervical spine near the C7 transverse process. The SG thus is a major sympathetic switching and transit station for the "fight-or-flight" response; interrupting this complex circuitry with a local anesthetic could have observable effects on conditions mediated by similar responses, such as PTSD.

[name] et al. (2014) (including two other authors involved in this trial, [name] and [name]) recently reported a case series of 166 patients, by far the largest in the literature. The PTSD Checklist – Military (PCL-M) was administered a day before treatment and repeated at 1 week and 1, 2, and 3-6 months post-SGB. An improvement in PCL-M scores of  $\geq 10$  was observed in 73.5% of the 132 patients evaluated at 3-6 months. 24 subjects who had a positive response for at least 3 months and then had the return of symptoms were treated with a second SGB; their PCL-M response trends were similar to those with their first SGB.

These findings support the need for a randomized, blinded, sham-procedure-controlled trial to rigorously study the effectiveness of SGB for treatment of PTSD symptoms.

## **1. PURPOSE OF THE ANALYSIS PLAN**

This statistical analysis plan (SAP) contains detailed information about statistical analyses to be performed to evaluate the effectiveness of SGB applied at weeks 0 and 2 for treatment of PTSD symptoms. This study also includes an acceptability portion, which focuses on participants' perception of SGB in relation to other PTSD treatments. This SAP does not include statistical analysis for the acceptability portion of this study. Additional statistical analyses not included here may be done to support manuscript preparation but these will not require an update to the SAP.

## **2. STUDY OBJECTIVE AND OUTCOMES**

### **2.1. STUDY OBJECTIVES**

The primary study objective of the effectiveness study is to evaluate whether right-sided SGB performed at 0 and 2 weeks will reduce PTSD symptoms which will be reflected in the improvement of the CAPS-5 total symptom scores between baseline and 8 weeks. Data analysis will be performed according to the intent-to-treat principle. The primary outcome of this study (difference in CAPS-5 total syndrome score from baseline) will be tested for differences between arms.

Secondary objectives include:

1. to evaluate whether right-sided SGB performed at 0 and 2 weeks will improve PTSD symptoms as reflected by corresponding PCL-5 items across time
2. to explore the association between the main outcome and potential confounding variables (e.g., concomitant medications, duration of PTSD, post-block Horner's syndrome, etc.)

3. to evaluate whether right-sided SGB performed at 0 and 2 weeks will reduce distress (K6), suicidality (M.I.N.I.-Plus Suicidality), anxiety (GAD-7, PHQ-9) and pain (short pain scale) across time
4. to evaluate whether right-sided SGB performed at 0 and 2 weeks will improve physical and mental (SF-12) condition across time

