## PROTOCOL SYNOPSIS

**RTI International**  
**[name]**  
**Research Triangle Park NC 27709**

---

**Title of Study:** A Randomized, Sham-procedure-controlled, Blinded Study to Evaluate the Effectiveness and Acceptability of Right-sided Stellate Ganglion Block for Treatment of Posttraumatic Stress Disorder Symptoms

---

**IND Number:** This is a non-IND study.

**EudraCT Number:** This is a non-EU study

---

**Study Centers Planned:** 2 centers in USA  
1 center in Germany

---

**Effectiveness Objectives:** The primary objective of the clinical effectiveness trial is as follows:

- to evaluate whether right-sided stellate ganglion block (SGB) performed at 0 and 2 weeks will result in a 10 point decrease in the mean Clinician Administered PTSD Scale for DSM-5 (CAPS-5) total symptom scores between baseline and 8 weeks

The secondary objectives of the clinical effectiveness trial are as follows:

- to evaluate whether right-sided SGB performed at 0 and 2 weeks will improve PTSD symptoms as reflected by corresponding PTSD Checklist for DSM-5 (PCL-5) items between baseline and 8 weeks
- to explore the association between the main outcome and other potential confounding variables (e.g., concomitant medications, duration of Posttraumatic Stress Disorder [PTSD], post-block Horner's syndrome, etc.)
- to evaluate whether right-sided SGB performed at 0 and 2 weeks will reduce distress (K6), suicidality (M.I.N.I.-Plus Suicidality), anxiety (GAD-7), depression (PHQ-9), alcohol use (AUDIT-C/AUDIT), or pain (short pain scale) between baseline and 8 weeks
- to evaluate whether right-sided SGB at 0 and 2 weeks will improve physical and mental condition (SF-12) between baseline and 8 weeks

---

---

---

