## 2. OBJECTIVES

### 2.1. Clinical Effectiveness Trial

The primary objective of the effectiveness study is:

- to evaluate whether right-sided SGB performed at 0 and 2 weeks will improve the CAPS-5 total symptom scores between baseline and 8 weeks

The secondary objectives of this study are:

- to evaluate whether right-sided SGB performed at 0 and 2 weeks will improve PTSD symptoms as reflected by corresponding PCL-5 items between baseline and 8 weeks
- to explore the association between the main outcome and potential confounding variables (e.g., concomitant medications, duration of PTSD, post-block Horner's syndrome, etc.)
- to evaluate whether right-sided SGB performed at 0 and 2 weeks will reduce distress (K6), suicidality (M.I.N.I.-Plus Suicidality), anxiety (GAD-7), depression (PHQ-9), alcohol use (AUDIT-C/AUDIT) or pain (short pain scale) between baseline and 8 weeks
- to evaluate whether right-sided SGB performed at 0 and 2 weeks will improve physical and mental (SF-12) condition between baseline and 8 weeks

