#### 6.2.3.5. *AUDIT-C/AUDIT (Appendix 8)*

The Alcohol Use Disorders Identification Test (AUDIT; Babor, Higgins-Biddle, Saunders, & Monteiro, 2001) will be used to assess potential alcohol abuse symptoms. The instrument was developed as a means of brief assessment and screening for excessive drinking. This 10-item scale is widely used and has been shown to be consistent with ICD-10 definitions for alcohol dependence and harmful alcohol use (Allen, Litten, Fertig, & Babor, 1997; Saunders, Aasland, Amundsen, & Grant, 1993).

The AUDIT-C (AUDIT alcohol consumption questions) consists of the first 3 items of the full AUDIT and assess frequency of drinking, typical quantity, and frequency of heavy drinking. In order to decrease participant burden, we will administer the AUDIT-C first; only those screening positive on these items will receive the remaining 7 items of the full AUDIT. It is administered in support of secondary objective 3.

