### 8.2. Secondary Analysis

The treatment effect on the clinical criteria of PTSD as measured by the PCL-5 over time will be assessed at weeks 2, 4, 6 and 8 using a generalized-linear mixed model to account for temporal correlation between weekly measures and the clustering of the data; this model will control for treatment, week, site, baseline PCL-5 score and the two way interaction between treatment and time. The outcome variable will be a binary variable denoting positive diagnosis. Because the psychometric properties of this instrument are still under development, details of the cut point definitions will be described more fully in the Statistical Analysis Plan (SAP), based on either published results of those psychometric studies currently ongoing, or preliminary psychometric analyses of data from this study, as deemed most appropriate when the SAP is developed. Adjusted and unadjusted probabilities of benefit of treatment at each time point will be produced using contingency table analysis (log-likelihood chi-square) and generalized-mixed models, correspondingly.

Effects of treatment on individual items from the PCL-5 through time will be evaluated descriptively using shift tables and shift frames. Details of these descriptive analyses will be included in the SAP.

Treatment effect in the improvement or reduction of relevant health and psychological status information such as suicidal thoughts (M.I.N.I.-Plus Suicidality), psychological distress (K6), anxiety disorders (GAD-7), depression (PHQ-9) and pain (short pain scale) will be analyzed using similar modeling techniques with either linear mixed models or generalized models used appropriately for the structure of the outcome measure (continuous, binary, ordinal, nominal). Each model will incorporate treatment, baseline measure, site, and time as categorical variables and two-way interactions between treatment and time and appropriate confounding variables. Models exploring change through time will account for the repeated measures (longitudinal) and clustering effects (participants). Models evaluating the different scores at different time points will account for the site effect, baseline measure and concomitant variables and comorbidities relevant to the different outcomes.

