### **2.3.2. PCL-C (PTSD symptoms)**

This standardized assessment comprised 17 items corresponding to the key symptoms of PTSD from the DSM-IV. The total symptom severity score ranges from 17 to 85. The PCL-C has been thoroughly validated and deemed reliable (Weathers, Litz, Herman, Huska, & Keane, 1994). The PCL-C will be administered at baseline in order to establish a baseline score in support of secondary objective 1.

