#### **2.3.4. AUDIT-C/AUDIT.**

The Alcohol Use Disorders Identification Test (AUDIT; Babor, Higgins-Biddle, Saunders, & Monteiro, 2001) will be used to assess potential alcohol abuse symptoms. The instrument was developed as a means of brief assessment and screening for excessive drinking. This 10-item scale is widely used and has been shown to be consistent with ICD-10 definitions for alcohol dependence and harmful alcohol use (Allen, Litten, Fertig, & Babor, 1997; Saunders, Aasland, Amundsen, & Grant, 1993). Scores range from 0 to 40, with scores between 8 and 15 (inclusive) suggest a medium level of alcohol problems, scores ranging from 16 to 19 represent a high risk of alcohol problems, and scores of 20 or greater warrant further diagnostic evaluation for alcohol dependence.

The AUDIT-C (AUDIT alcohol consumption questions) consists of the first 3 items of the full AUDIT and assess frequency of drinking, typical quantity, and frequency of heavy drinking. Based on a scale of 0 to 12, a score of 4 or greater is considered positive in males, while a score of 3 or more is positive among females.

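### Alcohol use is a protocol secondary objective and a listed SAP outcome, but the SAP drops the objective and specifies no analysis for it

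*SAP*

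**What the plan says.** **Alcohol use in the protocol.** Section 2.1 sets out to evaluate whether SGB reduces several outcomes, ending with "depression (PHQ-9), alcohol use (AUDIT-C/AUDIT) or pain (short pain scale) between baseline and 8 weeks". The Synopsis carries the same objective: "depression (PHQ-9), alcohol use (AUDIT-C/AUDIT), or pain (short pain scale) between baseline and 8 weeks". Protocol 6.2.3.5 and 6.4.5 tie AUDIT-C/AUDIT to secondary objective 3 and repeat it at weeks 4 and 8. Table 1 also shows it at screening and baseline.

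**Alcohol use in the SAP.** SAP 2.3.4 lists the AUDIT among the secondary outcome measures and says it "will be used to assess potential alcohol abuse symptoms". SAP section 3 keeps it in the schedule at weeks 0, 4 and 8. The third objective in SAP 2.1, however, says only that SGB "will reduce distress (K6), suicidality (M.I.N.I.-Plus Suicidality), anxiety (GAD-7, PHQ-9) and pain (short pain scale) across time". Alcohol is absent and no reason is given.

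**Analysis sections.** Protocol 8.2 covers suicidality and K6, then "anxiety disorders (GAD-7), depression (PHQ-9) and pain (short pain scale) will be analyzed", with PCL-5 and SF-12 treated in neighbouring paragraphs. SAP 8.6.3 covers the same group. Neither names the AUDIT.

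**PCL-C.** SAP 2.3.2 states: "The PCL-C will be administered at baseline in order to establish a baseline score in support of secondary objective 1". Protocol Table 1 collects it at screening and at weeks 0, 2, 4, 6 and 8. SAP 8.6.2 models PCL-5 alone.

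**The concern.** A SAP should carry every protocol objective through to a defined endpoint and model, or say why it does not. Here the objective, the instrument and the visits all exist, but the chain breaks at the SAP objective and is not picked up in the analysis sections. Whether and how alcohol use is reported is then settled after the data are seen. SAP section 1 allows additional analyses without a SAP update, so that choice need leave no record.

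The choice is not trivial for this instrument. It can yield an AUDIT-C score, a positive screen or a full AUDIT total, and because administration is gated these do not have the same set of observed participants.

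The status of the two measures is also unclear. SAP 8.4 treats as exploratory only those outcomes not described among the primary or secondary outcomes. AUDIT and PCL-C are described there, so by that rule they are not exploratory, yet they have no analysis of their own.

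**Working it through.** No stated figure is at issue. The check matches each listed measure to a named analysis.

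| Measure (SAP 2.3) | Named in SAP 8.6 | Named in Protocol 8.2 |
|---|---|---|
| 2.3.1 PCL-5 | 8.6.2 | yes |
| 2.3.2 PCL-C | no | no |
| 2.3.3 M.I.N.I.-Plus | 8.6.3 | yes |
| 2.3.4 AUDIT-C/AUDIT | no | no |
| 2.3.5 K6 | 8.6.3 | yes |
| 2.3.6 PHQ-9 | 8.6.3 | yes |
| 2.3.7 GAD-7 | 8.6.3 | yes |
| 2.3.8 SF-12 | 8.6.3 | yes |
| 2.3.9 Pain scale | 8.6.3 | yes |

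Listed: 9. Named in SAP 8.6: 1 (in 8.6.2) + 6 (in 8.6.3) = 7. Without a specified analysis: 9 − 7 = 2. Protocol 8.2 names the same seven.

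Protocol objective 3 has six domains: distress, suicidality, anxiety, depression, alcohol use and pain. SAP objective 3 keeps five of the six instruments, with PHQ-9 placed under anxiety. The missing one is the AUDIT. The SAP addenda concern CAPS-5 response, CAPS-5 diagnosis, a subgroup analysis and missing CAPS-5 data. They restore neither measure.

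**Which alcohol endpoint is usable.**

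1. Protocol 6.2.3.5 asks the three AUDIT-C items of everyone, after which "only those screening positive on these items will receive the remaining 7 items of the full AUDIT".
2. SAP 2.3.4 sets a positive AUDIT-C at 4 or more for men and 3 or more for women, on a 0 to 12 scale.
3. A ten-item total is therefore collected only at visits where AUDIT-C is at or above that threshold, and neither document gives a rule for scoring the items not asked.
4. A man who moves from 4 at week 0 to 3 at week 8 has improved by 4 − 3 = 1 point on AUDIT-C, but has a ten-item total only at week 0.
5. If the total were put into the SAP 8.6.2 form of model without a scoring rule, his week 8 value would be missing. A man at 3 at week 0 would have no baseline covariate, so all his visits would be lost.
6. SAP 8.3 plans no imputation for secondary outcomes. Addendum 2 relies on missing at random for the mixed models, but here the same visit's AUDIT-C score decides whether the total is observed, and a model of the total alone does not contain that score.

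AUDIT-C is free of this because every participant is asked its items at weeks 0, 4 and 8. The documents do not give the proportion expected to be AUDIT-C positive, so the amount of missing totals cannot be estimated.

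**The case against.** The strongest reply is that the plan is not silent. The Synopsis sends other secondary outcomes to mixed or generalised models according to the type of outcome. The instrument lists in Protocol 8.2 and in the text of SAP 8.6.3 are introduced by *such as*, so they are open. SAP 8.2 promises summaries of the data by treatment group. A reader might infer that alcohol use and PCL-C will never be analysed or reported, and these passages do not support that. What remains is that they supply at most a model class: no endpoint, no scoring rule and no time points. The heading of SAP 8.6.3 lists its measures by name, without *such as*, and includes neither.

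Second, no passage proposes the AUDIT total as an endpoint, and SAP 2.3.4 already describes AUDIT-C as a scale with cut-offs. That is correct. The loss of improving participants would arise only if the total were chosen later without a scoring rule. It is a reason to name the endpoint, not a defect the plan has already committed.

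Third, PCL-C appears in no objective: objective 1 names only PCL-5 in both documents. PCL-C also serves as the eligibility screen. Protocol 6.2.3.3 explains its use partly by the PCL-5's lack of psychometric and change data at the time, and SAP 8.6.2 now cites a PCL-5 cut-point of 33. This stands, and it makes PCL-C much the weaker half of the point.

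**Conclusion.** The point holds for alcohol use as a mismatch between protocol and SAP: a current protocol objective is omitted from the SAP objectives without explanation, and its instrument, still listed and collected, has no specified analysis. The size is one of six domains in protocol objective 3 and, with PCL-C, two of nine measures in SAP 2.3. The primary CAPS-5 result is not touched. It should be corrected, but it does not threaten the trial's main conclusion.

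A reader might go further and take the omission as a decision to suppress an outcome, or give PCL-C the same standing as alcohol use. The documents give no reason for the omission, and no objective depends on PCL-C, so neither inference is supported. For PCL-C the gap is an outcome listed under objective 1 with no stated role beside PCL-5. It is also absent from the SAP section 3 schedule.

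The verdict assumes that the protocol objective as it now reads is still in force. The preference for AUDIT-C rests only on the gated administration described in the protocol.

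**What to change.** 1. Restore alcohol use to objective 3 in SAP 2.1 and to SAP 8.6.3, and name it in Protocol 8.2. Endpoint: AUDIT-C score (0 to 12) at weeks 4 and 8. Analysis: a mixed model suited to the distribution of the score, with week 0 AUDIT-C, site, time as a category, treatment and treatment-by-time.
2. Report the full AUDIT descriptively only, among those who were asked all ten items, with the number at each visit by arm.
3. If the omission was intended, record and justify removal of the objective, and make Protocol 2.1, the Synopsis and SAP 2.3.4 agree.
4. For PCL-C, either add the total score to SAP 8.6.2 as a supportive analysis ranked below PCL-5, or declare it descriptive. If it is modelled, put site in the model: the 8.6.2 equation contains site but the PROC MIXED model statement leaves it out, so the code should not be copied as it stands.
5. Both existing addenda were written after unblinding. Any analysis added after that point must be labelled post hoc in the SAP and in the report.

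The cost is SAP wording and at most two further models on data already collected. The post hoc label is the real price of adding them late.
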